15.	PATIENT CONFIDENTIALITY & DATA PROTECTION	54
16.	GUIDELINES AND APPLICABLE DOCUMENTS	55
17.	REFERENCE	56

	QMS document Nerivio TCH-008 Clinical Study Protocol	Doc ID: TEC0250 Revision #: 3.0 Page: 8 of 58
--	--	---

1. Synopsis

Title	A prospective, randomized, double-blind, sham-controlled multi-center clinical study assessing the safety and efficacy of Nerivio for the preventive treatment of migraine.
Investigational Device	Nerivio is an FDA-approved remote electrical neuromodulation (REN) device for the acute treatment of migraine with or without aura. Nerivio delivers transcutaneous electrical stimulation to the upper arm to induce conditioned pain modulation (CPM) that activates a descending endogenous analgesic mechanism. The treatment is self-administered and controlled by a smartphone application. The study will assess Nerivio for the preventive treatment of migraine using a 45-minute treatment given every other day.
Objectives	To evaluate the safety and efficacy of Nerivio for migraine preventive treatment.
Participant Population	Adults (18-75) meeting the International Headache Society criteria (ICHD-3) for migraine with or without aura, with 6-24 headache days per 28-day period and at least 4 days fulfilling ICHD-3 criteria for migraine without aura (code 1.1; C and D) or with aura (code 1.2; B and C), probable migraine, or requiring the use of triptans or ergot derivatives.
Sample size	Up to 375 participants
Inclusion Criteria	
 1. Age 18-75 years old 2. Must have at least a 6-month history of headaches that meet the ICHD-3 diagnostic criteria for migraine with or without aura, either chronic or non-chronic migraine. 3. History of 6 to 24 headache days per 28-day period for each of the 3 months preceding study enrolment (based on patient report). 4. Subjects on prophylactic migraine treatment are permitted to remain on 1 medication with possible migraine-prophylactic effects if the dose has been stable for at least 2 months prior to the screening visit, and the dose is not expected to change during the course of the study. 5. Have personal access to a smartphone (24/7). 6. Must be able and willing to comply with the protocol. 7. Must be able and willing to provide informed consent.
Exclusion Criteria	
 1. An active implanted electrical and/or neurostimulator device (e.g. cardiac pacemaker, cochlear implant).

	
2. Uncontrolled epilepsy.3. History of use of opioids or barbiturates on more than 4 days a month in the last 6 months.4. Current participation in any other interventional clinical study5. Participants without basic cognitive and motor skills required for operating a smartphone.6. Pregnant or breastfeeding.7. Other significant pain, medical or psychological problems that in the opinion of the investigator may confound the study assessments.8. Prior experience with the Nerivio device.
Study Design	
A prospective, randomized, double blind, sham controlled, multicenter trial, conducted in three phases. The trial will consist of a screening/enrollment visit, followed by a 4-week (28 days) baseline phase. Eligible participants will enter an 8-week double-blind preventive treatment phase. Following the preventive treatment phase, patients will be offered to participate in a 4-week open label pre-emptive treatment phase or continue their prevention treatment with an active device, according to their eligibility.
 
Patients will complete an electronic diary throughout the study; this includes a daily evening report (completed regardless of whether the patient had a headache) and a treatment feedback during the follow up pre-emptive phase
 
Phase I – Baseline - 4 weeks (weeks 1 through 4):
 
Eligible participants will install the Nerivio app on their smartphones and will be instructed to record daily their migraine/headaches symptoms and medication use on the Nerivio app.
 
Transition to the treatment phase:
 
Participants who meet the following criteria in the baseline phase will be eligible to continue to the treatment phase:
 
• Complete the diary in at least 22 out of the 28 days during the baseline phase (80%)• Have between 6 to 24 headache days during the 28-day baseline period.• At least 4 of their headache days during the baseline phase fulfill the ICHD-3 criteria for migraine (migraine without aura [code 1.1; C and D] or with aura [code 1.2; B and C], or probable migraine, or headaches

requiring the use of migraine-specific medications including triptans, gepants or ergot derivatives)

Phase II - treatment phase (prevention) – 8 weeks (weeks 5 through 12):

Participants who meet the baseline phase requirements will be randomized in a 1:1 ratio to active and sham groups. Participants will be instructed to complete a daily diary (in the Nerivio app) about their headaches, associated symptoms, and medication use. They will also be instructed to conduct a 45-minute treatment with Nerivio every other day.

Transition to the follow-up phase (open label):

At the end of the treatment phase, participants from both arms (active and sham) may continue to a follow-up phase in which they will receive an active device that can be used during this phase. The data of all participants will be used for safety analyses.

The data of participants from the baseline and treatment phases will be used to assess their eligibility to participate in the pre-emptive follow-up phase.

Participants eligible for the follow-up phase meet the following conditions:

- Between 6-16 headache days during the baseline phase.
- Participants experience prodrome symptoms within 24 hours prior to the onset of their migraine headache in at least half of their migraine attacks during the baseline phase.
- Participants completed the daily questionnaires in at least 70% of the days during the treatment phase.
- Treated every other day in at least 24 and less than 33 days during the 56 days of the treatment phase.

Phase III – Follow-up phase (open label) - 4 weeks (weeks 13 through 16):

All participants will receive an active Nerivio device to use during the follow-up phase. Participants who do not meet the above requirements will be able to enter into the safety follow-up and continue to use Nerivio every other day for the preventive treatment of migraine. They will be instructed to complete a daily diary as was done in the treatment phase.

	
Participants who meet the above requirements will enter the pre-emptive follow-up phase and be instructed to conduct a 45-minute device treatment within 60 minutes of prodrome symptom onset. Participants will be instructed to complete questionnaires regarding their headache, prodrome symptoms, and medication use at baseline (start of treatment), 2 hours post-treatment, and 24 hours post-treatment. In addition, participants will be instructed to continue to report the daily diary, as performed in the other phases of the study.

Primary efficacy endpoint	
Mean change in number of migraine headache days per month comparing the 4-week baseline phase (weeks 1 through 4) with the last 28 days of the treatment phase (weeks 9 through 12).
 
A migraine headache day is defined as a calendar day with headache that is accompanied by at least one of the following symptoms: aura, photophobia, phonophobia, nausea and/or vomiting; or a calendar day with a headache that is treated with a migraine-specific acute medication.

Secondary efficacy endpoints	
1. Mean change in number of moderate/severe headache days per month comparing the 4-week baseline phase (weeks 1 through 4) with the last 28 days of the treatment phase (weeks 9 through 12) A moderate/severe headache day is defined as a calendar day with moderate or severe headache.2. Mean change in the number of headache days per month from the 4-week baseline phase (weeks 1 through 4) to the last 4 weeks of the treatment phase (weeks 9 through 12). A headache day is defined as a calendar day with headache (at any severity).3. Percentage of patients achieving at least 50% reduction from baseline in the mean number of headache days (all severities) per month in the last 4 weeks of the treatment phase (weeks 9 through 12).4. Mean change in the HIT-6 total score from baseline to the last 4 weeks of the treatment phase (weeks 9 through 12).5. Mean change in the MSQ role function from baseline the last 4 weeks of the treatment phase (weeks 9 through 12).
Exploratory efficacy endpoints	
1. Reduction in the mean number of acute headache/migraine medication days per month in the last 4 weeks of the treatment phase (weeks 9 through 12) compared to Baseline (weeks 1 through 4). An acute headache/migraine medication day is a calendar day on which the

	
patient consumes at least one dose of any medication (OTC or prescribed) for acute treatment of headache or migraine.
 
[Endpoints 2-6 below relate to the pre-emptive follow-up phase]
 
2. Percentage of patients who treat for the first treatment in the pre-emptive phase, during a prodrome, when they are pain free, and remain pain free during the following 2 hours after the treatment, without use of acute medication.3. Percentage of patients who treat for the first treatment in the pre-emptive phase, during the prodrome, when they are pain free, and remain pain free during the following 24 hours after the treatment, without use of acute medication.4. Percentage of patients who treat for the first treatment in the pre-emptive phase, during the prodrome, when they are pain free, and remain either pain free or with mild pain during the following 24 hours after the treatment without use of acute medication.5. Mean change in the percentage of prodromes which were followed by a headache within 24 hours from baseline to the end of the pre-emptive follow-up phase.6. Mean change in the average number of moderate/severe headache days per month in the pre-emptive phase compared to the 4-week baseline phase. 
[Endpoint 7 relate to Health Economics analysis]
 
7. Differences between active and sham groups in reduction of the following events from baseline (weeks 1-4) to the last 4 weeks of treatment phase (weeks 9-12): (a) Absenteeism, (b) Presenteeism, (c) Healthcare provider appointments, (d) ED/ER visits, (e) Brain MRI/CT scans 
[Endpoint 8 relate to migraine prediction analysis]
 
8. Feasibility of a migraine prediction algorithm: Analysis of the daily information provided by the participants during the baseline period (weeks 1-4) for the purpose of predicting their migraine days
Safety endpoints	
1. The incidence of adverse events in general and by seriousness, severity and association to the device.2. Treatment tolerability (by electronic patient report).

theranica	QMS document Nerivio TCH-008 Clinical Study Protocol	Doc ID: TEC0250 Revision #: 3.0 Page: 13 of 58
------------------	--	--

Datasets	
1. Intent to treat analysis set (ITT) The ITT analysis set includes all randomized participants2. Modified intent to treat analysis set (mITT) The mITT analysis set includes all ITT participants who had at least 22 days of efficacy assessments in the last 4 weeks of the treatment phase (weeks 9 through 12) and at least 12 treatments performed throughout weeks 9-12.
Data Analysis	The ITT analysis set will be used for the safety assessments and the mITT analysis set will be used for the efficacy assessments.

	QMS document Nerivio TCH-008 Clinical Study Protocol	Doc ID: TEC0250 Revision #: 3.0 Page: 14 of 58
--	--	--

2. BACKGROUND

Migraine is one of the most prevalent and disabling neurologic disorders [1]. The International Headache Society defines migraine as a recurrent headache disorder manifesting in attacks lasting 4-72 hours. In addition to the disabling pain attacks, migraines can be either with or without aura, and accompanied by at least one of the symptoms: nausea, photophobia and phonophobia. Some patients also experience additional symptoms occurring hours or days before the headache, known as the prodromal phase, or after pain resolves, known as the postdromal phase. The prodrome symptoms include food cravings, repetitive yawning, fatigue and neck stiffness.[2].

Patients experiencing a frequent number of migraine attacks and a myriad of related symptoms require a treatment regime to manage their pain levels and extensive accompanying symptoms. Current treatment strategies for migraine consists of both preventive treatment and acute treatment. Preventive treatments have been shown to be efficacious for patients in reducing the number and severity of headache days, making it the primary treatment plan for chronic migraine patients [3].

However, current preventive treatments demonstrate only up to 50% response rate [4-6] and only 30% adherence rate [7], requiring additional new preventive treatments for these non-responders. Moreover, even when highly effective, preventive treatments do not prevent all migraine attacks, thus requiring the use of acute treatment [8], and if used excessively, acute medications can often lead to medication overuse headache (MOH) [9]. Thus, there is a great unmet to have a preventive treatment that does not increase medication intake on one hand, and on the other hand reduces the number of headache days and pain severity.

This unmet need can be met using remote electrical neuromodulation (REN) [10]. REN is a novel acute migraine treatment which stimulates upper arm peripheral nerves to induce conditioned pain modulation (CPM) - an endogenous analgesia mechanism in which conditioning stimulation inhibits pain in remote body regions [11]. The safety and efficacy of REN (Nerivio®, Theranica Bio-Electronics LTD., Israel) have already been established for acute treatment [12,13]. Nerivio was assessed for migraine in a randomized, double-blind, sham-controlled multi-center study (NCT03361423). This study demonstrated that REN provides superior clinically meaningful relief of migraine pain and MBS compared to placebo, offering a safe and effective non-pharmacological alternative for acute migraine treatment. Specifically, the active stimulation was more effective than sham stimulation in achieving pain relief (66·7% [66/99; CI_{95%} 56·48-75·82] vs. 38·8%, p<0·001), pain-free (37·4% vs. 18·4%, p<0·005) and MBS relief (46·3% vs. 22·2%, p<0·001) at 2 hours post-treatment, and that the pain relief and pain-free superiority of the active treatment was sustained 48 hours post-treatment. In addition, the incidence of device-related adverse events was low and similar between treatment groups (4·8% vs. 2·4%, p=0·49). All device-related adverse events were mild, did not required medical intervention and resolved

	QMS document Nerivio TCH-008 Clinical Study Protocol	Doc ID: TEC0250 Revision #: 3.0 Page: 15 of 58
---	--	--

within 24 hours. The device was granted a 510k De novo approval (DEN180059) for the acute treatment of migraine in people who do not have chronic migraine. In addition, two open label studies of the Nerivio for acute treatment of migraine in chronic migraine patients demonstrated similar patterns of pain relief, pain free and consistency of pain relief across treatments. Based on these studies, the device was granted a 510k pre-market notification (K201824) for the acute treatment of migraine in people 18 years and older.

The aim of the present study is to evaluate the safety and efficacy of Nerivio for a preventive treatment of migraine, thus establishing Nerivio as a digital health tool offering a complete treatment management of migraine. Since already demonstrated to be effective for acute treatment, Nerivio can provide a complete management of migraine pain and symptoms that will greatly benefit the quality of life of migraine patients, improving adherence and lowering the side effects.

3. IDENTIFICATION AND DESCRIPTION OF THE DEVICE INFORMATION

3.1. Intended use

Current indication for use of the device:

The Nerivio is indicated for acute treatment of migraine with or without aura in patients 18 years of age or older. It is a prescription use, self-administered device for use in the home environment at the onset of migraine headache or aura.

This study aims to expand the current indication to include the preventive treatment of migraine in patients 18 years of age or older.

3.2. Contraindications

- The device should not be used by people with congestive heart failure (CHF), severe cardiac or cerebrovascular disease.
- The device should not be used by people with uncontrolled epilepsy.
- The device should not be used by people with active implantable medical device, such as a pacemaker, hearing aid implant, or any implanted electronic device. Such use could cause electric shock, electrical interference or serious injuries or medical conditions.

Main warnings and precautions:

- The device should not be used over skin conditions, such as open wounds or rashes, or over swollen, red, infected or inflamed areas or skin eruptions or fragile skin on the upper arm at the treatment location.
- The device should not be shared with other people. The device is intended to be used by a single person to avoid skin disease or any transmissible disease.

	QMS document Nerivio TCH-008 Clinical Study Protocol	Doc ID: TEC0250 Revision #: 3.0 Page: 16 of 58
--	--	--

- The device should not be used on the heart, chest, neck, head or any other body location other than the upper arm, because this could cause severe muscle spasms resulting in closure of your airway, difficulty in breathing, or adverse effects on heart rhythm or blood pressure.
- The device has not been evaluated for use in pregnant women and people less than 18 years of age

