6.1.1. Inclusion criteria

- Age 18-75 years old
- Must have at least a 6-month history of headaches that meet the ICHD-3 diagnostic criteria for migraine with or without aura, either chronic or non-chronic migraine.
- History of 6 to 24 headache days per 28-day period for each of the 3 months preceding study enrolment (based on patient report).
- Subjects on prophylactic migraine treatment are permitted to remain on 1 medication with possible migraine-prophylactic effects if the dose has been stable for at least 2 months prior to the screening visit, and the dose is not expected to change during the course of the study.
- Have personal access to a smartphone (24/7).
- Must be able and willing to comply with the protocol.
- Must be able and willing to provide informed consent.

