6.1.2. Exclusion criteria

- An active implanted electrical and/or neurostimulator device (e.g. cardiac pacemaker, cochlear implant).
- Uncontrolled epilepsy.
- History of use of opioids or barbiturates on more than 4 days per month in the last 6 months.
- Current participation in any other interventional clinical study.
- Participants without basic cognitive and motor skills required for operating a smartphone.
- Pregnant or breastfeeding.
- Other significant pain, medical or psychological problems that in the opinion of the investigator may confound the study assessments.
- Prior experience with the Nerivio device.

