6.3. Procedures

This study includes up to four visits. Each visit can be performed either on-site or remotely, using a teleconference software. The means of remote visits will be documented in the site binder prior to site initiation. Each visit will have a time window of 10 days after the perspective visit date to complete the study visit.

Pre visit evaluation-

A candidate patient for the study will be asked by the clinic to complete an online questionnaire that will assess the patient compliance to participate in the study. A summary of the questionnaire will be sent to the clinic for review. The PI will use the data from the questionnaire to evaluate the patient ability to comply with the study requirements.

First visit –

The first visit will include screening, enrollment and training on the application.

Enrollment: The screening process will include an eligibility assessment and a urine pregnancy test. Following successful screening, the site staff will provide the participants

	QMS document Nerivio TCH-008 Clinical Study Protocol	Doc ID: TEC0250 Revision #: 3.0 Page: 33 of 58
---	--	--

with study related information, perform an enrollment interview and receive an informed consent from the participants. During this visit, participants will complete baseline questionnaires that includes information on frequency of migraine attacks, typical associated symptoms, use of preventive and acute treatments, and the effect that their migraine attacks have on their daily routine and quality of life (HIT-6 and MSQ questionnaires).

Application training: Eligible participants who enroll to the study will be trained to use the application that will be installed on their own smartphones. The participants will be instructed to complete a daily diary that included information on, headache with time of onset, migraine symptoms, and medication use. The site personnel will be required to document the training session in the CRF.

Baseline phase:

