After the enrollment visit, participants will undergo a 4-week baseline phase aimed to collect headache days, medication use, migraine symptoms, and further assess eligibility. Participants will use the app daily to record headache with time of onset, migraine symptoms and medication use. To ensure compliance, the app will send daily reminders/notifications in a pre-specified time in the evening chosen by the participant, but the questionnaire will be available throughout the day. The daily reports will be transferred by the application to the electronic data capture (EDC) system, where they will be collected and registered.

Qualification to enter into the treatment phase: Participants who complete the diary in at least 22 out of the 28 days during the baseline phase (80%), have between 6 to 24 headache days during the 28-day baseline period, at least 4 of their headache days during the baseline phase fulfill the ICHD-3 criteria for migraine (migraine without aura [code 1.1; C and D], or with aura [code 1.2; B and C], or probable migraine, or headaches requiring the use of migraine-specific medications such as triptans, gepants or ergot derivatives) will continue to the treatment phase. Participants who fail these criteria will be excluded from the study and considered screen failure.

Second visit-

Device training: Eligible participants who successfully complete the baseline phase will be randomized in a 1:1 ratio into one of the two groups: either active (treatment with Nerivio active device) or sham group (treatment with Nerivio sham device). During this visit, participants will receive general instructions on study procedures, device mode of operation and warnings/precautions. After the training, patients will be instructed to use the device at home every other day.

The site personnel will be required to document the training session in the CRF. If the visit is conducted remotely, the devices will be shipped/mailed to the participant beforehand, with clear instructions not to open the device before the training.

	QMS document Nerivio TCH-008 Clinical Study Protocol	Doc ID: TEC0250 Revision #: 3.0 Page: 34 of 58
---	--	--

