All other patients will be offered to receive an active device and continue in a safety follow-up, using Nerivio for preventive treatment of migraine, as instructed in the treatment phase.

Follow-up phase (open label):

Participants who continue into this 4-week period of follow-up phase, will receive an active device. Those who do not meet the requirements (see above) will use Nerivio for preventive treatment of migraine, as performed during the treatment phase. Participants will continue to complete a daily diary and use the device every other day for 45 minutes.

Participants who meet the requirements (see above) will receive the device for preemptive treatment of migraine. Participants will be instructed to use Nerivio within 60 minutes of prodrome symptoms onset, prior to the start of a headache, for a 45-minute treatment. The participants will be instructed to complete questionnaires regarding their headache, prodrome symptoms, and medication use at baseline (start of treatment), 2 hours post-treatment and 24 hours post-treatment. In addition, participants will be instructed to continue to complete the daily diary as in the baseline and treatment phases.

Participants will be permitted to take their usual care medications during this phase, except for the timepoint between starting a device treatment until 2 hours after treatment start.

Fourth (final) visit – End of study:

During the final visit, participants may be asked to fill additional questionnaires on their migraine and their experience with the device. In addition, all study devices will be returned to the clinic, either in person or by mail/shipment.

Study design is summarized in Figure 4 below.

[figure not shown]

Figure 4: Study design

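### One of the three device contraindications in Section 3.2 (heart failure, severe cardiac or cerebrovascular disease) is not an exclusion criterion, and no screening step refers to Section 3.2

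*Combined protocol and SAP*

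**What the plan says.** Section 3.2 gives three contraindications. The first is: "The device should not be used by people with congestive heart failure (CHF), severe cardiac or cerebrovascular disease". The second is uncontrolled epilepsy and the third is an active implanted device.

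The synopsis and Section 6.1.2 carry the same eight exclusions. Uncontrolled epilepsy is one of them and an active implant is another. None names heart failure, other cardiac disease or cerebrovascular disease. The nearest item is discretionary: "Other significant pain, medical or psychological problems that in the opinion of the investigator may confound the study assessments". The age criterion in Section 6.1.1 is "Age 18-75 years old".

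Section 6.3 describes how patients get from first contact to a device:

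- **Pre-visit questionnaire:** "The PI will use the data from the questionnaire to evaluate the patient ability to comply with the study requirements".
- **First visit:** "The screening process will include an eligibility assessment and a urine pregnancy test". An enrolment interview and baseline questionnaires on migraine history, treatments and quality of life follow.
- **Second visit,** where randomisation takes place: "participants will receive general instructions on study procedures, device mode of operation and warnings/precautions".
- **Third visit,** for those who do not qualify for the pre-emptive phase: "All other patients will be offered to receive an active device and continue in a safety follow-up".

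**The concern.** The protocol states that certain patients should not use the device, but its entry rules do not keep all of them out. Enrolment is decided against the listed criteria. Section 3.2 is part of the device description, and nothing in Section 6 refers back to it. A coordinator working from Sections 6.1 and 6.3 could enrol a patient with heart failure or a severe cardiac or cerebrovascular condition without departing from either section.

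What is at stake is the safety of individual participants. The upper age limit of 75 means that candidates with these conditions can reasonably be expected to present. The concern does not extend to power, the type I error rate or the estimate of the primary effect.

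**Working it through.** The plan states no figure on this point, so the check is a comparison of text followed by a short exposure calculation.

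**Contraindications against exclusions**

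| Section 3.2 contraindication | Matching exclusion in the synopsis and Section 6.1.2 |
|---|---|
| Heart failure, severe cardiac or cerebrovascular disease | None |
| Uncontrolled epilepsy | Yes |
| Active implanted device | Yes |

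Two of three are matched and one is not. The pacemaker given as an example in the implant exclusion reaches only those cardiac patients who have an active implant.

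Section 3.2 also says, as precautions, that the device has not been evaluated in pregnancy or below 18 years. Both precautions are enforced at entry: pregnancy by an exclusion and a urine test, age by an inclusion criterion. The unmatched contraindication is worded more strongly than these precautions and yet has no entry criterion of its own. The protocol gives no reason for the difference.

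**Steps that might close the gap**

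- The pre-visit questionnaire is used to judge the patient's ability to comply.
- The first-visit eligibility assessment is made against a list that lacks the item. The urine test addresses pregnancy only.
- The enrolment interview has no stated content.
- The baseline questionnaires cover migraine frequency, symptoms, treatments, HIT-6 and MSQ.
- Qualification for the treatment phase depends on diary completion and on headache and migraine day counts.
- Warnings at the second visit are instruction to the participant and not a check on eligibility.
- The third-visit rules use headache days, prodromes, diary completion and number of treatments. Everyone else is offered an active device.
- The withdrawal reasons in Section 6.1.3 do not mention contraindications.

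None of these steps refers to Section 3.2 or to contraindications.

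**Scheduled exposure of one such participant**

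Inputs from the synopsis and Section 6.3: a 56-day treatment phase, a 28-day follow-up, one session every other day, 45 minutes per session.

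- Treatment phase: 56 / 2 = 28 sessions; 28 × 45 / 60 = 21.0 hours.
- Safety follow-up with every-other-day use: 28 / 2 = 14 sessions; 14 × 45 / 60 = 10.5 hours.
- Total: 28 + 14 = 42 sessions; 21.0 + 10.5 = 31.5 hours.

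In the active arm all 42 sessions deliver active stimulation. In the sham arm the first 28 are sham and the 14 follow-up sessions are active. A participant who qualifies for the pre-emptive phase treats at prodrome instead, so the follow-up count is then not fixed. These figures are the ordinary schedule of any participant. They measure exposure and do not estimate risk.

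**The case against.** The strongest reply is that the protocol already forbids this use. Section 3.2 belongs to the protocol, Section 10 requires devices to be used according to the protocol, and Section 9.2 treats any non-compliance with it as a deviation. On that reading the prohibition exists and has merely not been repeated. This is a fair account of the text. But a deviation is identified after the event, whereas an exclusion criterion prevents enrolment, and nothing links Section 3.2 to eligibility.

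Second, the discretionary exclusion could be applied. The study assessments include adverse events by seriousness and device association, and severe cardiac disease could cloud their attribution. Severe cerebrovascular disease could cloud headache or aura reports. An investigator could therefore exclude such patients as the criterion is written. It still depends on individual opinion, and its test is confounding rather than safety. Stable cardiac disease need not confound a headache diary.

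Third, warnings are given before home use begins, and instructions for use come with the device. Both are safeguards, but they leave it to the participant to recognise the problem, at the visit where randomisation takes place.

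Fourth, the eligibility form and the content of the enrolment interview are not shown and may include a suitable question. That is possible. However, Section 9.1 says that case report forms are not part of the protocol and can be changed without an amendment, so such a question would not be a protocol requirement.

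What stands from these replies is a limit on the claim: some or all investigators may exclude these patients in practice. The omission from the entry criteria remains.

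**Conclusion.** The concern holds. One of three stated contraindications is missing from the exclusion criteria, and no described screening step makes up for it. The text comparison supports this with high confidence. How often such a patient would actually be enrolled cannot be computed, because it depends on investigator practice and on forms that are not in the documents.

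The exposure figures assume that the participant keeps to the schedule and, for the total, that every-other-day use continues in the safety follow-up. No harm is demonstrated. This is a safety omission that should be fixed. It does not threaten the trial's inference.

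**What to change.** Add one exclusion to Section 6.1.2 and to the synopsis, either naming the conditions in the first contraindication of Section 3.2 or excluding anyone with any contraindication listed there. Keep all other exclusions as they are. Record the new criterion as its own item in the first-visit eligibility check.

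The cost is one line in a protocol amendment and one item on the eligibility form. A few more screen failures may follow; the documents give no basis for a number.
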